## 1. General information of the ONCOFIT study

### 1.1. Background and rationale

Most patients with colon cancer undergo surgery due to its potential for a cure. However, this procedure yields a stress response usually accompanied by postoperative complications. While prehabilitation programs are emerging as effective approaches to mitigate post-surgical disturbances, it is still unknown whether a multidisciplinary prehabilitation and postoperative rehabilitation can further reduce the incidence of postoperative complications.

### 1.2. Objective

The overall objective of the ONCOFIT randomized controlled trial is to determine the effects of a multidisciplinary prehabilitation (i.e., 4 weeks before surgery) plus postoperative rehabilitation (i.e., 3 months after surgery) program (PPP) on postoperative complications (as measured by Comprehensive Complication Index (CCI)) in patients undergoing resection of colon cancer.

The secondary aims are to:

- (i) Examine the effects of PPP compared to usual care on clinical prognosis.
- (ii) Examine the effects of PPP compared to usual care on functional capacity.
- (iii) Examine the effects of PPP compared to usual care on body composition.
- (iv) Examine the effects of PPP compared to usual care on fecal microbiota composition.
- (v) Examine the effects of PPP compared to usual care on patient-reported outcomes.
- (vi) Examine the effects of PPP compared to usual care on clinical and tumor parameters.
- (vii) Examine the effects of PPP compared to usual care on lifestyle patterns.
- (viii) Examine the effects of PPP compared to usual care on sleep quality.

[figure not shown]

## 2.2. Randomization

After concluding baseline assessments, eligible participants will be randomly assigned (1:1 allocation) to either the control or intervention group by means of computer generated simple, unrestricted randomization.

### 2.3. Sample size

In a previous study, a 17.3-point mean difference was detected in CCI between a group of patients who were physically inactive and a group who were regularly active, both undergoing colorectal cancer surgery (2). Therefore, this study sample size was estimated for an  $\alpha$  level of 0.05 and 90% power to detect a 17.3-point difference in CCI (primary outcome) between usual care and PPP groups, considering an  $\sigma$  of 25.2 (the CCI standard deviation of the group of participants who were physically inactive). Based on this data, a sample of 36 participants per group was considered sufficient for our analysis. However, assuming a 20% drop-out rate, we decided to recruit a total sample size of 45 participants for each study group. Thus, a total of 90 participants ( $n \approx 45$  women) will be enrolled in the ONCOFIT study.

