## 3. Statistical principles

### 3.1. Confidence and P values

All statistical tests will be two-tailed, with a significance level set at  $\alpha = 0.05$ . Corresponding 95% confidence intervals will be reported. No adjustments for multiplicity will be applied, as only one primary outcome has been pre-specified and all secondary and exploratory analyses are considered hypothesis-generating.

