### 5.2. Analyses methods

The main analyses for primary and secondary outcomes will follow the intention-to-treat approach. For the primary outcome, given the commonly observed non-normality distribution of the data in this fields, a Mann-Whitney U test will be used to compare the median CCI between the intervention and control groups. For secondary outcomes with a single time-point (e.g., hospital lenght of stay), comparisons between groups will also be conducted using Mann-Whitney U test. To assess whether the group allocation (intervention/control) influences the risk of postoperative complications (yes/no), a binary logistic regression model will be conducted. Regarding secondary outcomes at multiple time points, a linear mixed-effects models with individual measures of growth being modelled as the function of randomly assigned group, assessment time, and the interaction between group and time. Estimations will be performed using the restricted maximum-likelihood method, including an unstructured covariance matrix to adjust for within-participant clustering resulting from the repeated-measures design. This model will assume that missing values are missing-at-random.

Secondary analyses will be performed using the per-protocol approach, defined as attending >80% of the sessions offered to the intervention group.

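### The 90% power in SAP 2.3 does not describe the planned two-sided Mann-Whitney test, which under a normal shift has about 80–81% power at 36 per group and 88–89% at 45

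*SAP*

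**What the plan says.** Section 2.3 takes its effect size from an observational comparison in which "a 17.3-point mean difference was detected in CCI between a group of patients who were physically inactive and a group who were regularly active". It takes as the standard deviation a value "of 25.2 (the CCI standard deviation of the group of participants who were physically inactive". From these, with alpha 0.05, it sizes the trial for "90% power to detect a 17.3-point difference in CCI (primary outcome) between usual care and PPP groups", concludes that "a sample of 36 participants per group was considered sufficient for our analysis", and raises this to 45 per group for 20% drop-out. It names no test, no distribution and no sidedness.

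Section 3.1 supplies the sidedness: "All statistical tests will be two-tailed, with a significance level set at" 0.05. Section 5.2 supplies the test: "a Mann-Whitney U test will be used to compare the median CCI between the intervention and control groups". The reason given there is "given the commonly observed non-normality distribution of the data in this fields".

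Two other sections decide which sample size matters. Section 3.3 analyses all randomised participants for the primary analysis, and section 5.3 expects no missing data for prognostic variables because they come from medical records.

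**The concern.** The trial is sized on one quantity and tested on another. A mean difference and a single SD are the inputs for a comparison of means. A Mann-Whitney test responds to the probability that a patient in one arm scores lower than a patient in the other. The two agree closely if the scores are normal and the intervention shifts them bodily, but the plan chose the rank test because it does not expect normal scores.

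What is at stake is how the primary result is read. A non-significant Mann-Whitney result would be set against a claim of 90% power that the SAP has not derived for that test. In addition, the 17.3 points that motivated the trial would not be estimated by the planned primary analysis.

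**Working it through.** **Inputs.** Difference δ = 17.3, SD σ = 25.2, alpha 0.05, power 90%, 36 and 45 per group, 20% drop-out (all 2.3); two-sided (3.1); Mann-Whitney (5.2).

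**1. Reproduce the plan's 36.** For two means, n per group = 2[σ(z_alpha + z_power)/δ]².

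- Two-sided: 2 × [25.2 × (1.960 + 1.282)/17.3]² = 44.6, so 45 (46 by the t distribution).
- One-sided: 2 × [25.2 × (1.645 + 1.282)/17.3]² = 36.3, so 37 (38 by t).

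The stated 36 is close to the one-sided answer only. The drop-out step is correct: 36/0.80 = 45.

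**2. Power for a difference in means.** Power = Φ(δ/[σ√(2/n)] − z_alpha).

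- n = 36: δ/[σ√(2/36)] = 17.3/5.94 = 2.913. One-sided 89.8%; two-sided Φ(0.953) = 83.0% (81.9% by t).
- n = 45: 17.3/5.31 = 3.256. Two-sided Φ(1.296) = 90.3% (89.6% by t).

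**3. Power for the planned test under a normal shift.** The relative efficiency of Mann-Whitney is 3/π = 0.955, so n is multiplied by 0.955.

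| Per group | By efficiency | By simulation (6,000 trials) |
|---|---|---|
| 36 | 81.2% | 79.9% |
| 45 | 88.9% | 87.7% |

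For 90%, 44.6/0.955 = 46.7, so 47 evaluable patients per group.

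Split of the loss at 36 per group: 89.8 − 83.0 = 6.8 points from sidedness, and 83.0 − 81.2 = 1.8 points from the rank test.

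**4. Dependence on the shape of the scores.** The SAP gives no control mean, no share of patients scoring 0 and no severity distribution, so everything in this step is an assumption. CCI was set to 0 for an assumed share of controls and drawn from a gamma distribution capped at 100 for the rest. The control SD came out at 23.6–25.2 and the mean difference at about 17. The intervention acts on severity only, on the number of patients with complications only, or on both. There were 2,000 trials per cell, so the Monte Carlo standard error is at most about 1 point. Entries are two-sided Mann-Whitney power in % at 36 / 45 per group.

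| Control mean | Zeros | Severity only | Fewer patients with complications | Both |
|---|---|---|---|---|
| 20 | 30% | 85 / 91 | 100 / 100 | 100 / 100 |
| 25 | 30% | 83 / 90 | 98 / 100 | 94 / 97 |
| 30 | 30% | 83 / 92 | 90 / 96 | 88 / 95 |
| 20 | 50% | 49 / 57 | 100 / 100 | 95 / 98 |
| 25 | 50% | 50 / 60 | 88 / 95 | 88 / 93 |

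With Beta-shaped scores instead, severity-only power at 36 per group is about 45–76% for 30–50% zeros (individual shapes range from 43% to 77%). If only the number of patients with complications falls, it is 86% to almost 100%, depending on shape. In the severity-only cells of the table, a two-sided t-test at 36 per group has 97–100% power. The same mean difference can therefore be clear to a comparison of means and much less so to the rank test.

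**The case against.** **The rank test is not the main cause.** This stands. About 7 of the roughly 9 points lost at 36 per group come from sidedness. A reader might infer that choosing Mann-Whitney by itself undermined the design; under a normal shift it costs about 2 points.

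**The relevant number is nearer 45.** This largely stands. Sections 3.3 and 5.3 together imply that nearly all randomised patients will have a CCI. Under a normal shift the planned test then has 88–89% power, close to 90%. But section 2.3 attaches its 90% to 36, so the stated claim remains wrong as written.

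**The low figures rest on inputs the SAP does not contain.** This stands too. Simulations with 60% zeros and a pure severity effect give power of only about 27–31%, and a reader might infer that the trial could easily miss a full 17.3-point effect. That scenario is close to impossible. With 60% zeros and an SD of 25.2, the mean among controls with complications cannot exceed 25.2/√(0.6 × 0.4) = 51.4. A severity-only effect would need a fall of 17.3/0.4 = 43.3 points among them, which is at least 84%, with no complication prevented. Even at 50% zeros the ceiling is 50.4 and the required fall 34.6 points, at least 69%. The rationale in 1.1 speaks of lowering the incidence of complications, and under that mechanism power is about 90% or more in most of the distributions tried.

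**Restating power changes no decision.** Section 2.5 shows that recruitment has begun, so the number of patients will not change. What can change is how a null result is interpreted, and that is reason enough to correct the figure.

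**Conclusion.** The stated power is wrong as written for the planned test. With the plan's own difference, SD and two-sided alpha, and assuming a normal shift, Mann-Whitney has about 80–81% power at 36 per group and 88–89% at 45. The first figure needs no assumption about zeros to fall short of 90%, and most of that shortfall is sidedness.

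The further dependence on shape is real in direction but not fixed in size. With 30–50% zeros assumed, power at 36 per group is below 90% in every severity-only case tried: about 45–76% with Beta-shaped scores and 49–85% with gamma-shaped ones. It is about 90% or more in most cases where fewer patients have complications, the lowest being 86–88%.

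A reader might go further and infer that the trial is underpowered. The SAP does not support that: it gives no CCI distribution, power can lie on either side of 90%, and at 45 per group the normal-shift figure is close to the target. That 2.3 used a normal-theory formula is also an inference, from its two inputs and the near match to the one-sided answer.

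**What to change.** Keep 90 patients and the Mann-Whitney test. In section 2.3:

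- Name the test and the two-sided alpha, and replace the 90% at 36 per group with the power of that test at both sample sizes: about 80% at 36 and about 88% at 45 under a normal shift with SD 25.2.
- Add a range simulated under stated CCI distributions (share scoring 0 in each arm, and score distribution among the rest), and label these as assumptions. Include at least one case in which severity falls and one in which fewer patients have complications.

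In section 5.2, report the difference in mean CCI with a bootstrap 95% confidence interval beside the test, because 17.3 refers to that quantity.

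The cost is a short simulation, one additional reported estimate and a slightly less favourable power statement. Recruitment and trial procedures are unaffected.

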### 5.3. Missing data

The number of missing data will be reported, and patterns of missing data will be explored. Based on previous experience, no missing data are expected for prognostic variables, as these will be extracted from medical records and used unless the patient explicitly revokes consent. For other outcomes, we expect that missing data will be assumed as missing at random. Therefore, the linear mixed model analyses will appropriately account for missing data. Nonetheless, once data processing has been completed, we will formally re-evaluate this assumption.

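### 36 evaluable patients per group give about 82% power, not 90%, under the SAP's two-tailed test; the 36 matches only a one-sided 5% calculation

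*SAP*

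**What the plan says.** Section 2.3 bases the trial size on "90% power to detect a 17.3-point difference in CCI (primary outcome) between usual care and PPP groups", with alpha 0.05 and an SD of 25.2 taken from the physically inactive group of a previous study. It finds that "a sample of 36 participants per group was considered sufficient for our analysis" and then, "assuming a 20% drop-out rate, we decided to recruit a total sample size of 45 participants for each study group". So 36 is the evaluable number to which the 90% is attached, and 45 is that number plus the allowance for loss. Section 2.3 does not say whether the calculation was one-sided or two-sided.

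Section 3.1 settles that for the analysis: "All statistical tests will be two-tailed", at 0.05. No section makes an exception for the primary outcome. Section 5.2 names the Mann-Whitney U test as the primary comparison. On completeness, section 5.3 says that "no missing data are expected for prognostic variables, as these will be extracted from medical records", and section 2.7 groups CCI with the clinical prognosis outcomes.

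**The concern.** The stated inputs fix the required number, apart from small differences between formulas, and a two-sided calculation does not give 36. It gives 9 or 10 more per group, too many to put down to rounding or choice of formula. The 90% is therefore not a property of the test the SAP plans, at the sample size to which the SAP attaches it.

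This is the only justification of the trial's size, and it concerns the primary outcome. Readers weigh a null result by the power the trial claimed. If they believe the false-negative risk for a 17.3-point difference was 10% when it was about 18%, they will take a null result as stronger evidence against that difference than it is.

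A related question is which evaluable number the claim refers to. Section 2.3 budgets a 20% loss, while section 5.3 expects practically none for outcomes taken from medical records. The two readings give materially different power.

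**Working it through.** **Inputs.** Difference 17.3, SD 25.2 (used for both groups), alpha 0.05, power 90%, 36 evaluable and 45 recruited per group, all from section 2.3. Allocation 1:1 from section 2.2. Two-sided testing from section 3.1.

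**Formula (normal approximation).** n per group = 2 × (z_alpha + z_power)² × (SD/difference)². Here (25.2/17.3)² = 2.1218, and twice that is 4.2436.

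**Reproducing the plan's figure.**
- Two-sided 0.05, 90% power: (1.960 + 1.2816)² × 4.2436 = 10.507 × 4.2436 = 44.6, so 45. The t-test gives 45.6, so 46. The stated 36 is not reproduced.
- One-sided 0.05, 90% power: (1.645 + 1.2816)² × 4.2436 = 8.564 × 4.2436 = 36.3. The t-test gives 37.0. This is close to 36, although strict rounding up would give 37 or 38.
- Two-sided 0.05, 80% power: 33.3 (t-test 34.3). This does not give 36 either.
- Drop-out step: 36/0.8 = 45. This is correct.

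**Power at the stated numbers.** Power is approximately Φ(difference / (SD × √(2/n)) − z_alpha). At n = 36 the standard error is 25.2 × √(2/36) = 5.940, and 17.3/5.940 = 2.913. Two-sided, Φ(2.913 − 1.960) = Φ(0.953) = 83.0%. One-sided, Φ(2.913 − 1.645) = Φ(1.268) = 89.8%. At n = 45 the standard error is 5.313, the ratio is 3.256, and two-sided power is Φ(1.296) = 90.3%.

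| Analysed per group | Two-sided, normal | Two-sided, t-test | One-sided, normal | One-sided, t-test |
|---|---|---|---|---|
| 36 | 83.0% | 81.9% | 89.8% | 89.2% |
| 45 | 90.3% | 89.6% | 94.6% | 94.4% |

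**Detectable difference at 36 per group, two-sided, 90% power.** (1.960 + 1.2816) × 5.940 = 19.3 points (t-test 19.5), not 17.3.

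**Number needed for 90% power after 20% loss.** 45/0.8 = 56.25, so 57; 46/0.8 = 57.5, so 58. The plan recruits 45.

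**Planned test.** If the groups differ by a shift of normal data, the Mann-Whitney test has relative efficiency 0.955 against the t-test. Two-sided power is then about 80% at 36 and 88% at 45, and about 48 per group are needed for 90% (45.57/0.955 = 47.7). This is illustrative, because section 5.2 chooses the test on the expectation that CCI is not normal.

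**The case against.** The strongest reply is that the trial as expected to be analysed has about the power it claims. Section 3.3 puts all randomised participants in the intention-to-treat analysis, and section 5.3 expects complete data for outcomes of this kind. With 45 per group, two-sided power is 89.6% to 90.3%. The 18% false-negative risk arises only if the full 20% is lost. Planning for loss while expecting little is also prudent rather than contradictory, and the 95% confidence intervals promised in section 3.1 limit misreading of a null result.

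Much of this stands. The shortfall belongs to the 36-per-group statement, and it largely disappears on a comparison-of-means basis if no CCI value is lost. But section 2.3 attaches the 90% to 36, not to 45, and that statement is wrong. If the allowance is needed, power falls to about 82%; if it is not, 36 is not the number that supports the claim.

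The one-sided origin is an inference. A second-group SD of about 19.8 would also lead to 36 two-sided, as would taking 45 as the requirement and multiplying by 0.8. The text supports neither: it gives only one SD, and it goes from 36 to 45. The error does not depend on how 36 arose.

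A last objection is that 82% and 90% are comparison-of-means figures, while the planned test is Mann-Whitney. That is fair, and the corrected text should name its basis. It does not rescue 36, since no section claims a gain in efficiency from the rank test.

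**Conclusion.** The concern holds. Under the two-tailed 0.05 of section 3.1, with a difference of 17.3 and an SD of 25.2 in both groups, 36 per group give 81.9% power (t-test) or 83.0% (normal), about 7 to 8 percentage points below the stated 90%. The required evaluable number is 45 or 46 per group. About 90% is reached only if all 45 recruited per group contribute a CCI value. These figures rest on the comparison of means implied by the mean difference and SD in section 2.3. For the Mann-Whitney test under a normal shift they would be about 80% and 88%; for the actual distribution of CCI the documents give no basis for a figure.

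**What to change.** Keep the 90 patients and correct section 2.3 as follows:

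- State that the calculation is two-sided at alpha 0.05 and based on a comparison of means.
- Replace the 90% claim at 36 per group with about 82% for a 17.3-point difference and an SD of 25.2.
- Add that about 90% is reached only if CCI is obtained for all 45 per group.
- Reconcile with section 5.3. If CCI is expected to be complete from medical records, state the power on 45 per group and drop the claim that 36 suffice. If the 20% loss is thought realistic for CCI, let the 82% stand as the planned power.
- Note that the primary analysis is a Mann-Whitney test. If a figure for that test is given, state the distribution it assumes.

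This changes SAP wording only and needs no extra patients. The price is a less favourable stated power. Restoring 90% after a 20% loss would take about 57 to 58 per group (114 to 116 in total), which is not asked for here.

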### 3.3. Analysis population

We plan to use two analyses approaches:

- (i) Intention-to-treat: This dataset will be used for the primary analysis of all outcomes and will include all the randomized participants. They will be analyzed based on the group they were originally allocated.
- (ii) Per-protocol analyses: This dataset will be used for secondary analyses and will include participants with >80% of attendance.

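### The drop-out allowance in SAP section 2.3 does not match the all-randomised, record-based primary analysis; two-sided, 45 per group gives about 90% power only if drop-outs keep the full benefit

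*SAP*

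**What the plan says.** Section 2.3 plans for "90% power to detect a 17.3-point difference in CCI (primary outcome) between usual care and PPP groups". The difference is borrowed from an earlier cohort, in which "a 17.3-point mean difference was detected in CCI between a group of patients who were physically inactive and a group who were regularly active". The standard deviation is also from that cohort: "of 25.2 (the CCI standard deviation of the group of participants who were physically inactive". This leads to 36 per group, and then, "assuming a 20% drop-out rate, we decided to recruit a total sample size of 45 participants for each study group".

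Three other sections determine what happens to a drop-out in the primary analysis:

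- Section 3.3: the intention-to-treat set is used for the primary analysis of all outcomes. It "will include all the randomized participants. They will be analyzed based on the group they were originally allocated".
- Section 5.3: "no missing data are expected for prognostic variables, as these will be extracted from medical records and used unless the patient explicitly revokes consent". Section 2.7 groups the CCI with the clinical prognosis outcomes, so this covers the primary outcome.
- Section 3.1: "All statistical tests will be two-tailed, with a significance level set at" 0.05. Section 2.3 itself does not say whether its calculation is one- or two-sided.

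Section 2.3 does not define drop-out.

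**The concern.** Dividing by 0.80 is the right allowance when 20% of patients have no outcome and the remaining 80% show the full planned difference. Sections 3.3 and 5.3 describe a different situation, in which almost nobody is lost to the primary outcome. A patient allocated to PPP who stops attending is still counted in the PPP arm with a CCI from the records, possibly with less than the full effect. The cost of dropping out is then a smaller expected difference, and section 2.3 carries the full 17.3 points through unchanged.

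What is at stake is how the result is read. If the trial is reported as having 90% power for 17.3 points and the intention-to-treat comparison is not significant, readers may take that as stronger evidence against PPP than the design can give.

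**Working it through.** **Inputs.** Difference 17.3, SD 25.2, alpha 0.05, power 90%, 36 and 45 per group, 20% drop-out (all section 2.3); two-tailed testing (3.1); all randomised patients analysed as allocated (3.3); CCI from records (5.3). The share *b* of the benefit kept by PPP drop-outs is not in the SAP. It is taken as an assumption over the whole range 0 to 1.

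**Step 1: reproduce the plan.** Inflation: 36/(1 − 0.20) = 45, exact. Base size, normal approximation: n = 2 × (25.2/17.3)² × (z for alpha + z for power)², where 2 × (25.2/17.3)² = 4.244.

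- One-sided: 4.244 × (1.645 + 1.282)² = 36.3, so 36 to the nearest whole number (37 rounded up; 38 with the t distribution).
- Two-sided: 4.244 × (1.960 + 1.282)² = 44.6, so 45 (46 with the t distribution).

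The stated 36 therefore reproduces only as a one-sided calculation.

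**Step 2: expected difference when drop-outs are retained.** Only PPP drop-outs dilute the contrast: difference = 17.3 × [1 − 0.20 × (1 − b)].

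- b = 1: 17.30
- b = 0.5: 17.3 × 0.90 = 15.57
- b = 0: 17.3 × 0.80 = 13.84

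**Step 3: power.** Two-sample t-test with noncentrality = difference / (25.2 × √(2/n)) and 2n − 2 degrees of freedom. The denominator is 5.313 at n = 45 and 5.940 at n = 36.

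| Case | n analysed per group | Difference | Noncentrality | Two-sided power | One-sided power |
|---|---|---|---|---|---|
| Retained, all benefit kept | 45 | 17.30 | 3.26 | 89.6% | 94.4% |
| Retained, half kept | 45 | 15.57 | 2.93 | 82.6% | 89.7% |
| Retained, none kept | 45 | 13.84 | 2.61 | 73.1% | 82.6% |
| All 20% lost | 36 | 17.30 | 2.91 | 81.9% | 89.2% |

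Allowing for the extra variance of a mixed PPP arm lowers the zero-benefit two-sided figure only slightly, to about 72%.

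**Step 4: separate sidedness from dilution.** Compare within a column. On the SAP's lost-data reading, moving from a one-sided to a two-sided test takes power from 89.2% to 81.9% with no dilution at all. Dilution matters relative to that plan only when retaining drop-outs is worse than losing them. The two are equal when 1 − 0.20 × (1 − b) = √(36/45) = 0.894, which gives b = 1 − 0.106/0.20 = 0.47. Above about half the benefit, the nine extra patients per group more than offset the dilution. Below it, the further loss is at most 81.9 − 73.1 = 8.8 points two-sided, or 89.2 − 82.6 = 6.6 points one-sided.

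**Step 5: the planned test.** Section 5.2 specifies Mann-Whitney. If CCI were normal, with relative efficiency 0.955, the normal approximation gives about 89% (full benefit) and 72% (none) at 45 per group, two-sided. Section 5.2 itself expects non-normal data, so all these figures are approximations.

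**The case against.** The case for leaving section 2.3 alone has real substance. Drop-out is undefined: if it means patients with no usable CCI, such as those who revoke consent, then 36/0.80 is the correct inflation. The 17.3 points is put forward as the difference between the two arms and can be read as an intention-to-treat target that already allows for imperfect adherence. The programme starts 4 weeks before surgery (section 1.2), so a patient who leaves after surgery has already had the prehabilitation; zero retained benefit is an extreme case.

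All of this stands as a limit on how far the point goes. It does not remove the mismatch. If 20% are expected to lack a CCI, section 5.3 is wrong to expect no missing prognostic data; if they are not, section 2.3 applies the wrong kind of allowance.

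A reader might infer more: that dilution by itself leaves 45 per group underpowered, or that the inflation factor should have been 1/0.80² = 1.56. The SAP does not support either. The factor 1.56 holds only if every PPP drop-out gets no benefit, and the SAP says nothing about when patients drop out or what they retain. On the one-sided basis that reproduces 36, retaining all 45 with half the benefit still gives about 90%. A good part of the two-sided shortfall comes from the one-sided base figure and would be there without any dilution.

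**Conclusion.** The point holds as an inconsistency between section 2.3 and sections 3.1, 3.3 and 5.3, not as an arithmetic slip: 36/0.80 = 45 is exact. Under the SAP's own two-tailed, all-randomised analysis, 45 per group gives about 90% power only if retained drop-outs keep the whole 17.3 points. Power is about 83% at half the benefit, 73% at none, and 82% if all 20% are lost instead. A mixture of lost and retained patients is also possible, since consent revocations are true losses.

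Two causes act together: a base size that reproduces only one-sided, and no allowance for a smaller difference among retained drop-outs. The second adds to the SAP's own lost-data plan only if drop-outs keep less than about half the benefit. The figures rest on SD 25.2 in both arms, 20% drop-out in the PPP arm, an undocumented share of benefit kept, and a t-test standing in for Mann-Whitney.

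**What to change.** Keep 90 patients and the planned analysis. In section 2.3:

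- State whether drop-out means loss of the CCI or leaving the programme, consistently with section 5.3.
- State whether 17.3 points is meant as the intention-to-treat difference.
- Replace the unconditional 90% with the two-sided power over the full range: about 73% to 90% if drop-outs are retained and keep none to all of the benefit, and 82% if all 20% are lost.
- Label the benefit kept by drop-outs as an assumption, and say that 36 is a one-sided figure, so that the two causes are not confused.
- Note that the figures are t-test approximations to the planned Mann-Whitney test.

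The cost is wording only: no extra patients and no change to the analysis. The stated power becomes less favourable.
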